6.3 Methods and Timing for assessments

Schedules of assessments are listed in **Table No. 1 below**.

Table 1: Study visit schedule

Study Activities	Visit I: Screening and Inclusion	Visit II: Procedure At day of screening or within 30 days post screening	Visit III: Telephone Follow-up Up to 2 weeks ± 3 days from visit II
Informed Consent	X		
Demographic Data	X		
Medical History	X		
SNOT 22	X		
Concomitant medication related to sinus disease	X		
Physical Examination	X		
Vital Signs (optional)	X		
Inclusion/exclusion criteria	X		
CT scan (as available)	X (optional)		
Lund Mackay/Kennedy inflammation score	X		
Endoscopy with Peregrine and a standard Endoscope		X	
User questionnaire		X	
Patient tolerability and pain score		X	
AEs/SAEs		X	X
Patient Exit			X

7 STATISTICAL CONSIDERATIONS AND SAMPLE SIZE

Statistical Considerations

Demographic and baseline characteristics will be summarized for all subjects included in the analysis. Continuous variables will be summarized using summary statistics (mean, standard deviation, median, range combined with 95% confidence interval calculations) and categorical variables will be summarized using counts and percentages.

In particular, the following tests according to the parameters type are going to be performed:

- Continuous parameters will be presented by the estimated value and calculation of 95% confidence intervals. In addition, the comparison will be by using the relevant Student's t-test.
- Categorical parameters will be analyzed by Fisher exact test/ chi-square tests (in case of low observed frequencies).

Tests will be two-sided in accordance to the hypothesis regarding the tested parameters, with a significance level of 0.05.

Sample Size

Up to thirty (30) patients are expected to complete the study.

The primary endpoint of the study will be to demonstrate that the Peregrine Endoscope will perform comparable to or better than a Standard 70° 4mm Endoscope, where a difference of 20% or more between visualization success rates will be considered to be statistically significant. Per protocol, a subgroup analysis of each of the different sinus cavities (i.e., Frontal, Maxillary and Sphenoid) will be used for power calculation.

In order to maintain minimal Power 80% and Type I ($=\alpha$) error of 5% to detect minimal differences of $\pm 20\%$, a sample size of 7 samples is needed per sinus cavity. This number does not include an estimated 20-30% drop-out rate due to technical reasons unrelated to the device. Therefore, a sample size of 10 samples per each sinus cavity, and a total of 30 samples for all sinuses (total of up to 30 patients), will be recruited to the study.

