2 SYNOPSIS

Protocol Number	PG-001
Protocol Title	Safety and Effectiveness Evaluation of the Peregrine™ Drivable ENT Scope for Office Endoscopy of the Paranasal Sinuses in Patients who underwent ESS
Participating Centers	Emory University, Atlanta, GA
Clinical Phase	Open, single-center, prospective
Investigational Study Device	Peregrine™ Drivable ENT Scope, by 3NT Medical
Study Procedures	
Up to 30 Patients, out of which are at least 10 samples per each of the frontal, maxillary and sphenoid sinuses, who have had prior ESS and are scheduled for nasal endoscopy in the office as part of a routine post-operative office visit or due to recurrence of symptoms, will be evaluated with Peregrine Endoscope. The patients will attend the following visits:
 
 1. Visit 1: Screening and Enrollment – as part of a regular office visit 2. Visit 2: Sinonasal endoscopy – evaluation with Peregrine and standard endoscopes 
Visits 1 and 2 can be combined into a single visit.

Study Population	Patients who have had prior ESS
Study Purpose	To assess the safety and effectiveness of Peregrine endoscope in patients in the office setting in terms of access into and visualization of the paranasal sinus anatomy, image quality, patient tolerability and clinical utility.
Study Endpoints	
Primary – Performance and Safety Endpoints:
 
 • To compare visualization success rates of the paranasal sinus anatomy by Peregrine and by a standard endoscope used in the office setting. • Device related adverse events 
Secondary – Performance Endpoints:
 
 • To assess the adequacy of the image quality of Peregrine for endoscopy procedures in the office. • To evaluate patient tolerability and pain • To evaluate the impact of extended visualization by Peregrine on clinical workflow

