4.3 Study End Points

Primary - Safety

All adverse device effects will be captured and summarized as defined in **Section-8**. Adverse device effects (type, frequency, severity) are expected to be similar to those reported in the literature for Nasal Endoscopy (section 8).

For this study, the Safety comparison with the data of Nasal Endoscopy reported in the literature will be descriptive with no statistical endpoints.

Primary – Performance

Evaluation of ability of Peregrine and the comparison endoscope to access and visualize sinus anatomy at the following landmarks:

- Maxillary (ostium, anterior wall, lateral aspect, floor)
- Frontal (ostium, posterior wall, anterior wall, lateral recess)
- Sphenoid (ostium, sella, floor, lateral recess)

Subjects will be evaluated with:

- a. Mandatory – Peregrine Endoscope (the study device)
- b. Mandatory – A Standard 30° 4mm endoscope
- c. Optional – A Standard 70° 4mm endoscope
- d. Optional – A standard Flexible Endoscope

- Visualization success rates, calculated as the No. of successes divided by the No. of attempts, will be confirmed by direct visualization.
- Representative images of the accessed anatomic landmarks will be recorded.
- Level of prior resection will be recorded – anterior or posterior ethmoidectomy, draf IIa, draf IIb, uncinatectomy, antrostomy, maxillectomy, sphenoidotomy, dilation

Secondary - Performance

- Image quality – will be assessed through a yes/no statement regarding adequacy of Peregrine image quality for office endoscopy procedures, in comparison to the comparison device.
- Patient pain and tolerability will be assessed through validated VAS for both Peregrine and the comparison endoscope.
- Impact of Peregrine's extended visualization capability on clinical workflow will be evaluated through a series of questions regarding identification of pathology, evaluation of mucosa, change in medical management, need for additional CT scan, indication for revision surgery, etc.
- Peregrine ease-of-use will be evaluated through a user questionnaire.

Other Measurement – Performance and effectiveness

- Irrigation (through Peregrine working channel) will be documented (performed/not performed), when performed.
- To evaluate nasal cavity inflammation and sinuses inflammation using Lund Mackay CT score and Lund Kennedy Endoscopic scoring, if applicable.

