6 INVESTIGATION PLAN

6.1 Study Design

Type of Study

This is an open, single-center, prospective study in which the investigational device, the Peregrine Drivable ENT Scope, will be tested in a single group of adult patients, male or females.

The rationale behind this study is to show that the ability to visualize intra-sinus anatomic landmarks of the Maxillary, Frontal and Sphenoid sinuses is comparable to or better than the ability to visualize them with a Standard 70° 4mm Endoscope in the office setting; This study will evaluate the safety and performance of the Peregrine endoscope which enables intra-sinus visualization as a first step to assess potential benefits, such as minimizing CT scans and associated radiation exposure, change in medication regimen, referral to revision surgery, saving multiple office visits, and cost.

This study is proposed after completing a series of clinical cases with the Sinusway endoscopy system, (which is similar to the Peregrine Endoscopy system) which demonstrated that the system is safe and performed well to physician's satisfaction (detailed information on the studies is provided in the Investigator's Brochure).

Measures to Minimize Bias

Subjects shall constitute their own control group by comparing the ability to visualize intra-sinus anatomic landmarks and pain and tolerability between Peregrine and a standard endoscope in the same subject. For this reason, no randomization is necessary in this study.

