6.2 Study Procedures

Visits 1: Screening and Enrollment

- Screening will take place at the day of procedure or within 1 day-30 days before the procedure as part of a regular office visit.
- Patients who potentially qualify for the study will be offered an Informed Consent to sign prior to further evaluation. Any patients who do not qualify will be exited from the study as screening failures and will not be included in the safety/effectiveness analyses.
- The following assessments will be performed before the procedure for each patient:
 - Medical history (including concomitant medications deemed relevant by the investigator)
 - Sino-Nasal outcome test (SNOT-22)
 - Vital signs – optional
 - CT scan – optional - as available in the patient file.
 - Nasal Cavity and sinuses inflammation score will be captured using the Lund Mackay CT
 - Compliance with inclusion/exclusion criteria
 - Patients found eligible to participate in the study during visit 1 will be scheduled to undergo nasal endoscopy evaluation with Peregrine.

Visit 2: Procedure

The procedure will be office endoscopy as part of a routine post-operative office visit or due to recurrence of symptoms. Visits 1 and 2 can be combined into a single visit.

- **Before the procedure:**
 - Eligible subject/s will attend the Medical Center at the day of procedure and will be inquired by the PI regarding changes to their health status since the screening visit. If at this point it is

determined that the patient **does not** meet all Inclusion and Exclusion criteria and cannot be treated, the patient will be exited from the study. These patients will be considered screening failures and will not be included in any of the safety or efficacy endpoint analyses.

- **Endoscopy:**

1. Patients will undergo the procedure under local or topical anesthesia, at physician discretion.
2. The Peregrine endoscopy system will be prepared for use per its instructions for use.
3. Obligatory – the surgeon will attempt to visualize the pre-defined sinus anatomy landmarks with a standard 30° 4mm endoscope which will be recorded as success/failure, and an image of the anatomic landmarks visualized will be taken. Patient will be asked to score the endoscope for pain and tolerability.

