4. Obligatory – the surgeon will then attempt to visualize the pre-defined sinus anatomy landmarks with Peregrine endoscope which will be recorded as success/failure, and an image of the anatomic landmarks visualized will be taken. Patient will be asked to score Peregrine for pain and tolerability.
5. Optional – the surgeon will have the option to attempt to visualize the pre-defined sinus anatomy landmarks with a standard 70° 4mm endoscope and/or a flexible endoscope which will be recorded as success/failure, and an image of the anatomic landmarks visualized will be taken. Patient will be asked to score the endoscope for pain and tolerability.
6. Optional - irrigation of the nasal anatomy will be performed and recorded as Done/Not Done and which sinus was irrigated.
7. The physician will answer a set of questions related to endoscope usability and utility in clinical decision making in comparison to the standard endoscope.
8. The procedure will be recorded by site's AIDA system to enable the physician to perform assessments post procedure.

- **After the procedure:**

- The patient will recover from the procedure according to center's common practice. Before the patient is dismissed, recording of AE, if any, will be performed. Patient will exit the study.

Visit 3: Telephone Follow-up visit

- Telephone Follow-up for safety assessment will be conducted by study personnel two weeks \pm 3 days following patient last study visit.
- In the absence of any on-going ADE's, the patient will exit the study and Exit Form will be completed.

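### The two scopes are scored on the same landmarks in the same patients, but the plan names only unpaired tests for success/failure and does not define the unit of analysis

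*Combined protocol and SAP*

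**What the plan says.** **Design.** Section 6.1 makes the comparison within patient: "Subjects shall constitute their own control group by comparing the ability to visualize intra-sinus anatomic landmarks". It gives this as the reason for not randomizing. In Section 6.2, step 3, "the surgeon will attempt to visualize the pre-defined sinus anatomy landmarks with a standard 30° 4mm endoscope which will be recorded as success/failure"; in step 4, "the surgeon will then attempt to visualize the pre-defined sinus anatomy landmarks with Peregrine endoscope which will be recorded as success/failure".

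**Test.** For categorical outcomes, Section 7 and the synopsis name one approach: "Categorical parameters will be analyzed by Fisher exact test/ chi-square tests (in case of low observed frequencies". A t-test is named for continuous outcomes only. Tests are two-sided at 0.05.

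**Unit.** Section 4.3 lists four landmarks for each sinus and defines "Visualization success rates, calculated as the No. of successes divided by the No. of attempts". The synopsis counts differently: "at least 10 samples per each of the frontal, maxillary and sphenoid sinuses". Section 7 plans 10 samples per cavity and 30 in all, from up to 30 patients. Nothing says what one attempt or one sample is, or how many sinuses or sides a patient may contribute.

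**Aim and comparator.** Section 6.1 states the aim as "comparable to or better than the ability to visualize them with a Standard 70° 4mm Endoscope in the office setting", and Section 7 also names the 70° scope. The synopsis names the 30° scope for the same aim. Under Section 6.2, step 5, the 70° scope is optional: "the surgeon will have the option to attempt to visualize the pre-defined sinus anatomy landmarks with a standard 70° 4mm endoscope". Section 7 and the synopsis add that a gap of 20% or more between success rates will count as statistically significant.

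**The concern.** The design relies on pairing and the named analysis discards it. Fisher and chi-square compare two separate groups. Here the two results come from the same anatomy, often from several landmarks in one sinus, so they are correlated both between scopes and within patient.

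This is the primary performance comparison, and the text presents it as a demonstration with 80% power and 5% type I error. With the unit open, the analyst could count 10 sinuses or 40 landmarks per cavity after seeing the data, and the p-value depends on that choice. The aim is also one of comparability, which a non-significant difference test does not establish whatever the unit.

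**Working it through.** **Inputs from the documents:** 10 samples per cavity, 4 landmarks per sinus, two-sided 5%, a 20-point difference. **Assumed, because the documents give none:** success rates of 50-90% and all correlations.

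**1. The plan's own number.** The step from 7 to 10 reproduces: 7/(1 − 0.30) = 10. The 7 itself does not follow from the stated inputs. McNemar's test for a 20-point difference needs 37 to 96 pairs at an assumed discordance of 20% to 50%. The 10 is used below as the planned count.

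**2. One yes/no pair per patient per cavity.** Let both scopes have success rate p and within-pair correlation ρ. The cell probabilities are p² + ρp(1−p) for both succeeding, p(1−p)(1−ρ) for each discordant cell, and the remainder for both failing. The variance of the difference is 2p(1−p)(1−ρ)/n. The unpaired tests use 2p(1−p)/n, which is too large when ρ > 0. Summing the multinomial probabilities of all tables of 10 pairs with test p ≤ 0.05 gives the type I error at ρ = 0:

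| Success rate | Fisher | Chi-square, uncorrected |
|---|---|---|
| 50% | 1.3% | 4.2% |
| 70% | 1.2% | 3.7% |
| 90% | 0.1% | 0.9% |

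Positive ρ lowers every entry. Fisher exceeds 5% only near 50% success with ρ below about −0.6.

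**3. Landmarks pooled, 40 per cavity.** These are simulations from a latent-normal model at an assumed 70% success rate, with no true difference and Fisher at nominal 5%:

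| Assumed source of correlation (share of latent variance) | Type I error |
|---|---|
| Landmark difficulty shared by both scopes (0.6-0.8) | 0.1-0.5% |
| Sinus difficulty shared by both scopes (0.4) | 1.4% |
| Mixed: sinus 0.3, landmark 0.2, scope-specific 0.1-0.2 | 2-4% |
| Scope-specific clustering (0.2-0.4), ten patients | 6-10% |
| The same, five patients giving two sinuses each | 11-19% |

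Landmark-level McNemar does not cure the clustering. In a separate simulation with scope-specific shares of 0.3-0.6 it rejected in 9-17% of runs, against 7-15% for Fisher.

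**4. The test can change the result.** Take 28/40 against 34/40, with six landmarks seen only by Peregrine and none only by the comparator. Fisher gives p = 0.18. Exact McNemar gives 2/2⁶ = 0.031, taking the landmark pairs as independent.

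**5. The 20% sentence.**
- *As a decision rule on the observed difference:* at 10 against 10, Fisher p for a 20-point gap is smallest at 0/10 v 2/10 or 8/10 v 10/10, where it is 0.47. The rule therefore contradicts the 0.05-level test.
- *As a margin:* with no discordant pair, the lower limit of the paired score 95% interval is −z²/(n + z²) = −3.84/13.84 = −28 points at n = 10, so −20 is not excluded. Excluding it needs n > 4z² = 15.4, that is 16 pairs. The continuity-corrected Newcombe paired interval, also with full agreement, gives −16.7 at 5/10 successes and −17.6 at 6/10, which do exclude −20. At 8/10 or more it does not.

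**6. Comparator.** Every patient has a 30° and a Peregrine result by design. A 70° result exists only where the surgeon chose to obtain one. With fewer than six complete pairs exact McNemar cannot reach 0.05, since 2/2⁵ = 0.0625.

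**The case against.** The strongest reply is that the named tests do no harm. For single pairs with zero or positive correlation this is right: they keep the 5% level. A reader might infer from the 6-19% figures that the plan has an inflated type I error. The documents do not support that. Those figures need pooling that the plan does not specify and scope-specific correlation that nobody has measured, and other equally assumed settings give 0.1-4%. What remains is that the plan does not fix the unit under which the tests are safe, and conservatism does not help to show comparability.

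A reader might also infer that ten pairs can never meet a 20-point margin. That holds for the score interval at exactly ten single pairs, not for every paired interval, and the synopsis sets ten as a minimum.

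It could be said that chi-square may loosely include McNemar's version and that the t-test may be paired. Neither is stated. Fisher has no paired reading, and the t-test would reach this endpoint only if a per-patient proportion were defined. The reply does stand for the VAS scores, where a paired t-test may well be intended.

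Finally, paired tests are weak at this size. For a true 20-point difference, exact McNemar with 10 pairs has power of 0.6-3.9% over discordance of 20-50%. That is a reason to lead with the interval, not to keep an unpaired test.

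**Conclusion.** The point holds, and the change should be made before analysis. The mismatch between paired data and unpaired tests, and the missing unit, are read directly from the text and need no assumption. The size and direction of the error are not fixed. It is conservative with 10 single pairs (at most 1.3% for Fisher and 4.2% for chi-square at 50-90% success and correlation zero or positive). With pooling it ranges from about 0.1% to 19%, depending on assumed correlations. The case for changing the plan rests on the undefined unit and the unpaired method in the primary comparison, not on demonstrated inflation.

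**What to change.** In Section 7 and the synopsis:

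- **Unit.** Define it, and state how many sinuses per cavity a patient may contribute.
- **Method.** Replace Fisher/chi-square for between-scope comparisons.
  - *One pair per patient per cavity:* use exact McNemar with a named paired 95% interval, and say which governs. They can disagree: at 4:0 and 5:0 of 10 the score interval excludes zero (+1 to +69 and +8 to +76 points), while McNemar gives p = 0.125 and 0.0625.
  - *Landmarks or sinuses pooled:* use the within-patient difference in the proportion of landmarks seen, with a paired t-test and t-based interval or a pre-chosen sign-flip test. Do not use landmark-level McNemar that ignores clustering.
- **The 20%.** State whether it is a margin, a design effect size or a decision rule. If a margin, judge it by the lower limit of the named interval. If a decision rule, remove its conflict with the 0.05-level test.
- **Comparator.** Reconcile the 30° and 70° statements in the synopsis and Sections 6.1, 6.2 and 7, and say how missing pairs are handled if an optional scope is the comparator.

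**Cost.** No extra procedure is needed. It would be too much to say that no new data are needed: Section 6.2 does not say that success/failure is entered per landmark. If the CRF holds one entry per sinus, the landmark-proportion analysis needs a per-landmark field or scoring from the stored images and recordings.

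Power is also limited. In simulation of a true 70% against 90% with ten patients and four landmarks, the paired t-test had 35-78% power, against 53% for Fisher with landmarks treated as independent. The t-interval is approximate: at a true −20 points it wrongly cleared a 20-point margin in 2.0-5.7% of runs, against a nominal 2.5%. It should not be used if all differences are zero, when its width is zero.

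### The rule for choosing a categorical test gives sparse tables to chi-square instead of the exact test; at 7-10 samples per cavity this can change borderline verdicts, though it inflates type I error little

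*Combined protocol and SAP*

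**What the plan says.** Section 7 (Statistical Considerations) and the Statistical Analysis Plan row of the synopsis carry the same sentence: "Categorical parameters will be analyzed by Fisher exact test/ chi-square tests (in case of low observed frequencies". On sidedness and level, Section 7 adds "Tests will be two-sided in accordance to the hypothesis regarding the tested parameters", "with a significance level of 0.05".

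Under Sample Size, Section 7 bases power on each sinus cavity separately. It states that "a sample size of 7 samples is needed per sinus cavity", and raises this to "a sample size of 10 samples per each sinus cavity" to allow for "an estimated 20-30% drop-out rate due to technical reasons unrelated to the device". No other test is named for the success/failure comparison of the two scopes.

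Section 6.1 (Measures to Minimize Bias) makes each subject their own control. Section 4.3 defines the success rate as successes over attempts and lists four landmarks per sinus. It does not say whether an attempt is a sinus or a landmark.

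**The concern.** Fisher's exact test is meant for sparse tables. Chi-square relies on a large-sample approximation that is usually trusted only when expected counts are adequate. The sentence puts the low-count condition directly after chi-square. It also judges sparseness by observed counts and gives no cut-off. If the slash is read as leaving both tests open, there is no selection rule at all and the test could be picked after the data are seen. Either reading needs correcting.

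At stake is the per-cavity primary performance comparison, where samples are few enough for the form of the test to matter. A borderline result could be called significant only because the large-sample form was used.

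**Working it through.** **Inputs from Section 7.** 7 samples needed and 10 recruited per cavity, two-sided alpha 0.05. **Assumptions.** One success/failure result per sinus and scope; uncorrected Pearson chi-square. True success rates are not given, so a range is used.

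**The plan's own figures.** The drop-out step reproduces: 7/(1 - 0.30) = 10. The 7 does not reproduce as a two-proportion sample size. With [1.96√(2p̄q̄) + 0.842√(p1q1 + p2q2)]²/0.20², the need is 93 per device for 50% vs 70% and 35 for 80% vs 100%. That is a separate matter; 7 and 10 are taken here as the planned sizes.

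**Step 1: which branch applies?** With n per scope and S successes in total, the smallest expected count is min(S, 2n - S)/2.
- n=7: at most 7/2 = 3.5, so all 64 tables are below 5.
- n=10: it reaches 5 only when S = 10, which is 11 tables; 121 - 11 = 110 are below 5.

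**Step 2: do the two tests agree?** For 10/10 vs 6/10:
- Pearson: 20(10×4 - 0×6)²/(10×10×16×4) = 5.0, p = 0.025.
- Fisher: 2 × C(10,4)/C(20,4) = 2 × 210/4845 = 0.087.
- Yates: 20(40 - 10)²/6400 = 2.81, p = 0.094.

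All tables:

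| | n=7 | n=10 |
|---|---|---|
| Tables | 64 | 121 |
| Significant, uncorrected chi-square | 20 | 46 |
| Significant, Fisher | 12 | 34 |
| Different verdict | 8 | 12 |
| Yates differs from Fisher | 0 | 0 |
| Smallest significant difference, chi-square / Fisher | 4/7, 5/7 | 4/10, 5/10 |
| Maximum type I error, chi-square / Fisher | 5.7%, 1.3% | 4.2%, 1.3% |

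Every disagreement has chi-square significant and Fisher not. At n=7 these are all the tables with a 4/7 difference (7/7 vs 3/7: 0.018 and 0.070; 6/7 vs 2/7: 0.031 and 0.103). At n=10 they are some tables with a difference of 4/10 or 5/10 (9/10 vs 4/10: 0.019 and 0.057; 8/10 vs 3/10: 0.025 and 0.070). Type I error was maximised over a common success rate with the scopes treated as independent, as both named tests do.

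**Step 3: how often would it matter?** Chance of a disagreeing table, per cavity, under independence:

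| True rates | n=7 | n=10 |
|---|---|---|
| 90% vs 90% | 0.3% | 0.8% |
| 80% vs 100% | 2.9% | 8.8% |
| 50% vs 70% | 8.5% | 7.3% |
| 50% vs 100% | 27.3% | 20.5% |

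**Step 4: the paired form.** The scopes are compared within subject, so the natural test uses discordant pairs. With d pairs all one way, exact McNemar gives p = 2 × 0.5^d: 0.125 at d=4, 0.0625 at d=5, 0.031 at d=6. The large-sample form gives 0.046, 0.025 and 0.014. A result of 10/10 vs 6/10 must have d=4, all one way, so the exact paired p is 0.125. Carrying the low-count rule into a paired analysis would call this significant, with a conditional type I error of 12.5% when there are four discordant pairs.

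**The case against.** The sentence may be a slip of word order, and a statistician would probably apply it correctly. That is plausible, but the wording stands twice and supplies no threshold to fall back on.

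A reader might infer that the choice of test generally decides significance at these sizes. The documents do not support that. The tests agree in 56 of 64 and 109 of 121 tables, and below a difference of 4/7 or 4/10 neither is ever significant. That includes an observed difference of 2/10, although Section 7 says that "a difference of 20% or more between visualization success rates will be considered to be statistically significant". Disagreement also requires the uncorrected statistic, and the plan does not say which form it means. If both scopes succeed about 90% of the time, a conflicting table is rare.

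A reader might also infer a seriously inflated type I error. At these sizes uncorrected chi-square peaks at 5.7% and 4.2%, closer to the nominal 5% than Fisher's 1.3%. For the unpaired tests the plan names, preferring Fisher costs power. This objection stands.

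Nor can it be said that the tables will always be sparse. The synopsis makes 10 per sinus a minimum. If landmarks are the attempts, a cavity holds 4 × 7 = 28 to 4 × 10 = 40 results per scope. The tests can still disagree there (50 of 841 and 72 of 1,681 tables), but those results are clustered within sinuses and neither test allows for that.

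Finally, swapping the two test names would not repair the primary comparison, because both assume independent groups. This stands too, and shapes the fix.

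**Conclusion.** The rule is wrong as written and should be corrected, at moderate priority. It assigns the large-sample test to sparse data, uses observed counts, and sets neither a threshold nor a continuity correction. With one result per sinus and scope, that branch would cover nearly every per-cavity table. Reversed, the rule can only add significant results, in 8 of the 20 tables that uncorrected chi-square calls significant at n=7 (40%) and 12 of 46 at n=10 (26%).

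The harm is confined to borderline verdicts. It depends on an undefined unit of attempt and on the uncorrected statistic, and its frequency depends on success rates that the documents do not give.

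**What to change.** Replace the sentence in Section 7 and in the synopsis with two statements:
- The per-cavity comparison of Peregrine with the standard endoscope, being within subject, uses the exact McNemar test at every sample size.
- Other, unpaired categorical comparisons use Fisher's exact test when any expected count is below 5, and chi-square otherwise.

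Naming the exact paired test outright avoids a cut-off on discordant pairs, which would again leave room for choice. McNemar needs one success/failure result per sinus and scope, so the attempt must be defined alongside it.

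The drafting cost is one sentence in two places. The statistical cost is real: exact tests are clearly conservative here. Fisher's true size is about 1.3%. For exact McNemar at n=7, the conditional size is 3.1% with 6 discordant pairs, 1.6% with 7, and zero below 6. If pairs are discordant with probability 0.92, the overall size is 7 × 0.92⁶ × 0.08 × 0.0313 + 0.92⁷ × 0.0156 = 1.9%, its maximum. At least 6 discordant pairs in one direction are needed for significance.

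Because Section 7 aims to show performance comparable to or better than the standard scope, the plan should also say that a non-significant result does not show that the scopes are comparable.
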